The nature of the study will be explained to the participants and written informed consent will be obtained. Demographic data of each participant including age, sex, height, weight, BMI, percent body fat, lean body mass, and smoking history will be recorded. For people after stroke, the stroke type (cerebral infarction, intracerebral hemorrhage), medical history (hypertension, diabetes mellitus, cardiovascular disease, lipidemia, kidney disease) will also be recorded. The National Institutes of Health Stroke Scale (NIHSS), Modified Rivermead Mobility Index (MRMI), Modified Rankin Scale (mRS), Barthel index (BI) will be retrieved from the patient's medical record.

Participants will be invited to attend the cardiopulmonary laboratory of the hospital at a time > 2 hours after a light meal. Participants are requested to avoid caffeine-containing products, nicotine, alcohol and vigorous exercise for at least 12 hours before attending the laboratory.

Each participant will be asked to perform the lung function test to measure the FVC, FEV₁, and MIP after including the study. After completing the baseline lung function test, participant will be required to sit on the chair and rest for 15 minutes, after that, two trained researchers will use two identical ultrasonography to measure the left and right diaphragmatic thickness simultaneously at quiet breathing, the end of tidal inspiratory and the end of tidal expiratory, respectively. 3 ultrasonic images will be captured to calculate the mean diaphragmatic thickness of each breathing status. In order to determine the inter-rater reliability of the measurement of ultrasonography of

those two trained researchers, 20 participants will be chosen out randomly to receive twice diaphragmatic thickness measurement at quiet breathing, the end of tidal inspiratory and the end of tidal expiratory. However, during the second measurement, those two trained researchers will change their position to measure the contralateral side diaphragmatic thickness independently.

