After the baseline measurement, all participants will be requested to use a nose clip to hold the nose and breathe with the mouth through a pressure threshold inspiratory loading device (POWERbreathe, KH2, England). The inspiratory pressure will be set at 30%, 40%, 50%, 60%, 70%, or 80% of their MIP, in random order. Each MIP intensity protocol consists of 10 breaths. The procedure of IMT is followed by the published research protocols in people after stroke [28]. All MIP intensity protocols will be conducted in one day. A period of at least 10 minutes of rest time will be allowed between different protocols of contraction intensity (% MIP) on the same day [29].

Thickness of the left and right diaphragm (stroke and non-stroke), will be measured simultaneously by two identical ultrasonography at the end of maximum inspiration of 10 breaths of each MIP intensity protocol. The diaphragm thickness of both the left and right diaphragm at the end inspiratory breaths of the 10 breaths of each MIP intensity protocol will be recorded. Surface electromyography (sEMG) will be used to measure the activity of accessory muscle (sternocleidomastoid muscles) during each MIP intensity protocol. The % of MIP that associates with the highest calculated DTF and a relatively stable change in the activity of accessory muscles will be considered an appropriate training intensity for further IMT protocols.

The self-perceived exertion level will also be determined by the Rate of Perceived Exertion Borg scale at the end of each MIP intensity protocol [30].

All research procedures will be repeated again after 2 days to examine the test-retest reliability of ultrasonographic measurements of DTF.

Outcome measures:

[figure not shown]
Lung function

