Diaphragmatic thickness will be measured by the ultrasound machine (Mindray 9, Shenzhen, PRC). Ultrasonography is a portable, noninvasive emerging technique allowing easy and rapid estimation of muscle thickness [34, 35]. It not only can avoid the risk of exposure to radiation in medical facilities but also the reliability in providing a clear visualization of the muscle morphology at the zone of apposition [35, 36].

For consistency, all measurements will be conducted using the same transducer probe (model SuperLinear SL18-8; SuperSonic Imagine) with a bandwidth of 5 -18Hz of B mode. Ultrasonography will be performed by two trained physiotherapist who operates the machine under the guidance of a radiologist who is trained to use diagnostic ultrasound.

[figure not shown]
Participant needs to remain in the upright sitting position on the chair during the measurement procedure. To measure the right diaphragmatic thickness, the transducer probe will be placed in the right intercostal space above the eighth or ninth intercostal space, between the antero-axillary and mid-axillary lines with a 45° angle tilt between

the surface of the abdominal wall in the cephalic direction, where the diaphragm is most suitable visualized (shown in figure 1(a)). To measure the left diaphragmatic thickness, the transducer will be placed in the left intercostal space above the eighth or ninth intercostal space, between the anterior subcostal region between the anterior and midaxillary lines (shown in figure 2(a)). The diaphragm is observed as a three-layered structure, with the hypoechogenic muscular layer bordered by echogenic layers—the peritoneum and the diaphragmatic pleurae (as shown in figure 2(b) and figure 2(c)).

[figure not shown]
Figure 1 The placement of transducer probes, surface electromyography electrodes and image of the diaphragm

(a) The placement of transducer probes when measure of the right and left diaphragm by ultrasonography in people after stroke (left hemiplegia); The blue points represent the locations of surface electromyography electrodes on the sternocleidomastoid muscles.

[figure not shown]

(b) Diaphragmatic thickness images of the left diaphragm (stroke side) at the end of tidal expiration and the end of maximum inspiration at 30 %MIP.

(c) Diaphragmatic thickness images of the right diaphragm (non-stroke side) at the end of tidal expiration and the end of maximum inspiration at 30 %MIP.

Research flow chart

Reporting of adverse event:

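### Diaphragm thickness is scanned and measured at each load with no masking to load, cohort, side or session, although the highest DTF decides the training intensity

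*Combined protocol and SAP*

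**What the plan says.** All places are in the combined protocol and SAP, mostly in section 4, Research methodology.

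- **Who scans.** The measurement of diaphragmatic thickness: "Ultrasonography will be performed by two trained physiotherapist who operates the machine", guided by a radiologist.
- **Who measures at baseline.** Procedure: "two trained researchers will use two identical ultrasonography to measure the left and right diaphragmatic thickness simultaneously". For each breathing status, "3 ultrasonic images will be captured to calculate the mean diaphragmatic thickness of each breathing status".
- **Loads.** Procedure: "The inspiratory pressure will be set at 30%, 40%, 50%, 60%, 70%, or 80% of their MIP, in random order".
- **Measurement under load.** Procedure: left and right thickness "will be measured simultaneously by two identical ultrasonography at the end of maximum inspiration of 10 breaths of each MIP intensity protocol". No reader other than the two operators is named.
- **Images under load.** A caption to Figure 1 describes "Diaphragmatic thickness images of the left diaphragm (stroke side) at the end of tidal expiration and the end of maximum inspiration at 30 %MIP", so at least some loaded images are stored.
- **Decision rule.** Procedure: "The % of MIP that associates with the highest calculated DTF and a relatively stable change in the activity of accessory muscles" will be taken as the appropriate intensity.
- **Prior expectation.** The introduction (section 3) reports that in healthy adults and ventilated people the diaphragm's capacity is exceeded above 60% MIP, and that high intensity may lower diaphragmatic activity.

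The text does not mention blinding, masking, coded images or an independent reader. It does not say who sets the device, whether the setting is visible to the operators, or whether loaded thickness is read live or later from stored images.

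**The concern.** DTF is a ratio built from thicknesses that a person obtains by placing the probe, choosing a breath and frame, and placing calipers. Each step leaves room for judgement. If the person judging knows the load, a systematic difference between loads can enter the data without any difference in the diaphragm. The study selects a load by ranking DTF across loads, so a modest load-related bias could create or move the peak on which the recommendation rests.

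The planned safeguards address other problems:

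- Random load order protects against order and fatigue effects. It does not protect against a bias that follows the load itself.
- The inter-rater check covers 20 participants at quiet breathing, so it never tests loaded readings.
- The repeat after 2 days would reproduce a stable expectation bias and count it as agreement.

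**Working it through.** **What can be checked in the text.** Two operators scan during each loaded block. At baseline the researchers who scan also measure, and nothing assigns loaded readings to anyone else. No masking step appears. These facts support the inference that the reader knows the load, but no sentence says so.

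**The plan's own figures.** The plan gives no figure for reading bias. Its sample size is used here only to supply n and a yardstick.
- For effect size f = 0.2, alpha 0.05 and power 0.80, a within-subject ANOVA with six loads, correlation 0 and sphericity gives 55, close to the stated 54. The plan does not state the correlation or the number of measurements.
- 54 x 1.2 = 64.8, so 65 per cohort, and 2 x 65 = 130. Both match the plan.
- For a linear trend over six equally spaced loads with total rise B (in SDs), f = B x sqrt(35/12)/5 = 0.3416 B. The planned f = 0.2 is therefore a rise of 0.2/0.3416 = 0.59 SD.

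**Illustration 1: drift in millimetres.** Assumed, not from the documents: end-expiratory thickness 2.0 mm; between-person DTF SD 0.2 to 0.4; correlation between loads 0 or 0.5; sphericity; no true load effect; drift linear from 30% to 80% MIP and shared by all participants. From the plan: n = 65, six loads.
- DTF bias = drift/thickness = 0.1/2.0 = 0.05, or 5 percentage points.
- In SDs: 0.05/0.4 = 0.125 to 0.05/0.2 = 0.25, so f = 0.0427 to 0.0854.
- lambda = f² x 65 x 6/(1 - correlation), with 5 and 64 x 5 = 320 degrees of freedom. For f = 0.0854: 0.00729 x 390 = 2.84 at correlation 0, and 5.69 at 0.5.

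| Drift | Correlation 0 | Correlation 0.5 |
|---|---|---|
| none | 5% | 5% |
| 0.1 mm | 8.3-20.9% | 12.1-40.4% |
| 0.2 mm | 20.9-73.4% | 40.4-97.2% |

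At n = 54 the rates are lower. The 0.1 mm row becomes 7.7-17.7% and 10.7-33.6%.

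**Illustration 2: the ranking, which is what the decision uses.** Assumed: n = 54, no true effect, linear drift in SD units, correlation 0 to 0.8. With no drift, each load has a 1/6 = 16.7% chance of ranking highest.

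| Drift | ANOVA rejection | 80% MIP ranks highest |
|---|---|---|
| 0.1 SD | 6.7-14.8% | 27-40% |
| 0.2 SD | 12.6-52.7% | 38-59% |
| 0.3 SD | 24.5-90.4% | 47-72% |

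A drift of 0.3 SD is about half the 0.59 SD rise that the study is sized to detect.

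**What masked reading can recover.** If all drift arose at caliper placement, masked reading would return the rates to 5% and 16.7%. If half of a 0.2 SD drift arose at acquisition, 0.1 SD would remain and the rejection rate would still be 6.7-14.8%.

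**The case against.** The strongest reply is that the protocol is silent and does not choose unmasked reading. A team that hid the device setting and read coded images offline would break no sentence of it. This stands in part. A reader might infer that the operators are documented as knowing the load, but the text shows only who runs the machine and when. A reader might also infer that session 1 values are in view when session 2 is read, which would inflate the test-retest coefficient. The documents say only that the procedures are repeated. Neither stronger reading should be asserted. It remains true that a plan followed as written contains no protection.

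Second, the rates rest wholly on assumed inputs, and nothing in the documents shows that a 0.1 mm drift is small or plausible. The modelled drift also rises steadily to 80% MIP, whereas the protocol's own expectation is that the diaphragm's capacity is exceeded above 60% MIP. An expectation bias of that kind might pull the peak towards the middle loads instead. This objection stands. The figures show sensitivity and do not predict the bias.

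Third, it is tempting to say that masked reading would prevent the problem. It would remove the caliper-placement part only. Probe position, frame choice and coaching during the breaths are fixed at acquisition.

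Fourth, the reading load may be large. If all 10 breaths are read, 130 participants x 2 sides x 6 loads x 10 breaths x 2 sessions = 31,200 readings, before baseline images. If three images per load sufficed, it would be 9,360. However, the plan states the three-image rule only for baseline.

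**Conclusion.** The point holds as a cheap improvement to the design. The outcome that drives the choice of intensity depends on the operator, the plan provides no masking at acquisition or reading, and none of its existing checks would detect a bias that follows the load. Operator knowledge of the load is inferred, with medium confidence. Whether any bias would occur, how large it would be and which way it would run cannot be settled from the documents. The false-positive and ranking figures are illustrations under stated assumptions. The stated sample size is unaffected.

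**What to change.** 1. Store the baseline and loaded images or clips under codes assigned by a team member other than the two readers.
2. After both sessions, have the same two operators measure thickness offline in random order, masked to load, cohort, side and session. Use only these readings for DTF and for both intraclass correlation coefficients.
3. State who sets the device. Where feasible, have another team member who is already present set it out of the operators' view.
4. Fix in advance which breaths and frames are measured at each load. This limits selection at acquisition and also determines the reading workload.
5. Acknowledge in the protocol that bias from probe position or coaching may remain.

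**Cost:** image coding and offline reading time, with the amount set by step 4. No extra visits or participant procedures are needed. Coded storage has to be in place before the first participant, because acquisition cannot be masked afterwards.

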Research proposal

1. Project title

The effects of different inspiratory pressures on the diaphragmatic thickness fraction and sternocleidomastoid muscle activation in people after stroke

2. Abstract

This study is a cross-sectional study to determine the optimal inspiratory muscle training (IMT) intensity for stroke survivors. Participants will breathe through a pressure threshold inspiratory loading device with varying loads in random order. During the test, accessory inspiratory muscle (sternocleidomastoid muscles) activity will be measured with surface electromyography (sEMG) and diaphragm thickness will be used to assessed with ultrasonography. Repeated-measures ANOVA will be used for statistical analysis to determine the most effective training intensity.

3. Project objectives

Introduction:

Stroke was the second largest cause of global death and disability in 2019 [1]. Direct medical costs for stroke in China was 50 billion yuan (nearly 7.69 billion US dollars) in 2015, and this accounted for the highest medical cost in China [2]. In 2016, the Global Burden of Disease (GBD) study estimated that the lifetime risk of stroke from the age of 25 years was 39.3% in China, which is the highest estimated risk in the world [3]. In 2018, stroke was the third highest disease cause of death, accounting for 1.57 million deaths in China [4].

Stroke not only causes impairment of motor function but can also affect lung function [5]. The lung function (e.g. forced vital capacity (FVC), forced expiratory volume in one second (FEV1), maximal inspiratory pressure (MIP), peak expiratory flow (PEF)) in people after stroke was reported significantly lower than the age and gender-matched healthy adults [6, 7]. Impaired lung function in people after stroke not only leads to high risk of pneumonia, poor functional outcomes and prolonged hospitalization but may also increase mortality [8-10].

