Inspiratory muscle training (IMT) is an intervention designed for improvement of inspiratory muscle (including the diaphragm) strength and endurance in healthy adults and patients suffering from different diseases (e.g. Parkinson, chronic obstructive pulmonary disease, cardiovascular disease) [18-21]. Regarding the IMT training protocol, the commonly reported training intensities varied between 30-80% of MIP in people after stroke [22-24]. Although the diaphragm is the primary inspiratory muscle, the use of IMT may not help improve the diaphragmatic contraction under some circumstances. Previous studies suggested that, in healthy adults and people receiving mechanical ventilation, when inspiratory load exceeds the capacity of the diaphragm (higher than 60% MIP), the accessory respiratory muscle (in particular the sternocleidomastoid muscle) would be activated dramatically, which would increase work of breathing and fatigue [25, 26]. Other studies also reported that high IMT intensity may have the risk to increase the work of breathing thereby leading to fatigue [27] or resulting in a decrease, rather than increase, in surface electromyography signals in diaphragmatic activity [27]. It is postulated that IMT recruits accessory muscles such as sternocleidomastoid rather than diaphragm during the practice [24]. Hence, evaluation of effectiveness of IMT on DTF in people after stroke and further investigation on determining an optimal training protocol including inspiratory effort and training intensity for recruiting diaphragmatic activities in the stroke population are warranted.

Aims of the study:

To determine the optimal training intensity that is associated with the strongest diaphragmic thickening fraction in people after stroke.

Project significance:

Outcomes of this project study will fill the existing knowledge gaps in the understanding of the relationship between inspiratory pressure and recruitment of diaphragmatic muscles in people after sub-acute and chronic stroke.

4. Research methodology

Study design:

This study will be a cross-sectional study.

Participants:

Individuals who have had a stroke and healthy adults will be invited to participate in this study.

Participants recruitment for people after stroke:

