The inclusion criteria are: (1) age \geq 18 years; (2) clinically diagnosed with ischemic and/or hemorrhagic stroke; (3) duration of stroke range from 1 month to 12 months after diagnosis; (4) had no facial palsy, which could prevent proper labial occlusion; (5) had not undergone thoracic or abdominal surgery; (6) could understand and follow the verbal instruction; (7) stable cardiac conditions; (8) no previous history of respiratory problems.

The exclusion criteria are: (1) acute myocardial infarction or acute heart failure; (2) acute pain on chest or abdominal; (3) with the clinical signs of significant pulmonary disease; (4) consciousness impaired; (5) patient with nasal feeding tube, tracheal tube and/or any condition, which prevent the measurement or training.

Recruitment of healthy participants:

The inclusion criteria are: (1) age ≥ 18 years; (2) had not undergone thoracic or abdominal surgery; (3) no previous history of respiratory problems.

The exclusion criteria are: (1) acute myocardial infarction or acute heart failure; (2) acute pain in the chest or abdominal; (3) with the clinical signs of significant pulmonary disease; (4) unstable hypertension, arrhythmias, or unstable cardiovascular conditions, such as fluctuations in blood pressure and heart rate, indicate poor cardiac prognosis or the need for vasopressor medications; (5) pregnant.

Ethical approval:

Ethical approval will be sought from the Research Ethics Committee of Hong Kong Metropolitan University and Shenzhen Second People's Hospital.

Sample size calculation:

Sample size calculation will be based on the use of repeated-measures analysis of variance (ANOVA) using the G*Power 3.1. Considering an effect size of 0.2, an alpha error probability of 0.05 and a power of 0.80, the estimated sample size is 54 participants. An additional 20% of the sample size will be included to account for attrition. The final estimated sample size will be at least 130 participants (65 for each cohort).

Procedure:

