Though various measures will be taken to minimize the risk of adverse event throughout the study, any adverse events that might happen will be recorded.

Statistical analysis:

All data will be reported as mean \pm standard deviation (SD) unless otherwise indicated. Demographic data and clinical characteristics for all participants will be summarized using descriptive statistics. Repeated-measures ANOVA will be used to compare the differences of DTF and sEMG parameters determined at each inspiratory pressure separately. Intraclass correlation coefficient will be used to determine the inter-rater reliability of two ultrasonic operators and examine the test-retest reliability coefficient of ultrasonographic measurements of DTF recorded with different inspiratory pressures.

P value will be set at 0.05. All data will be analyzed using the IBM SPSS Statistics for Windows, Version 25.0 (Armonk, NY: IBM Corp).

References:

1. Gbd, S., Global, regional, and national burden of stroke and its risk factors, 1990-2019: a systematic analysis for the Global Burden of Disease Study 2019. *Lancet Neurol*, 2021. 20(10): p. 795-820.
2. Wu, X., et al., The hospital costs of stroke patients in Chinese island populations: an 11-year tendency analysis. *J Stroke Cerebrovasc Dis*, 2015. 24(5): p. 988-992.
3. Feigin, V., et al., Global, Regional, and Country-Specific Lifetime Risks of Stroke, 1990 and 2016. *N Engl J Med*, 2018. 379(25): p. 2429-2437.
4. Li X and Z. X., Annual data set on national mortality surveillance 2018. Beijing: China Science and Technology Press, 2019.
5. Menezes, K.K., et al., Respiratory muscle training increases respiratory muscle strength and reduces respiratory complications after stroke: a systematic review. *J PHYSIOTHER*, 2016. 62(3): p. 138-44.
6. Liu, X., et al., Assessment of Diaphragm in Hemiplegic Patients after Stroke with Ultrasound and Its Correlation of Extremity Motor and Balance Function. *Brain Sciences*, 2022. 12(7): p. 882.
7. Lista-Paz, A., et al., Pulmonary function in patients with chronic stroke compared with a control group of healthy people matched by age and sex. *Physiother Theory Pract*, 2022: p. 1-9.
8. Wilson, R., Mortality and cost of pneumonia after stroke for different risk groups. *J Stroke Cerebrovasc Dis*, 2012. 21(1): p. 61-67.
9. Saposnik, G., et al., Variables associated with 7-day, 30-day, and 1-year fatality after ischemic stroke. *Stroke*, 2008. 39(8): p. 2318-2324.

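### The six loads are compared only by repeated-measures ANOVA, with no rule for a missed load; a mixed model on all available first-session loads is a cheap improvement, not the correction of an error

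*Combined protocol and SAP*

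**What the plan says.** The Abstract states that "Repeated-measures ANOVA will be used for statistical analysis to determine the most effective training intensity". The Statistical analysis section repeats the method: "Repeated-measures ANOVA will be used to compare the differences of DTF and sEMG parameters determined at each inspiratory pressure separately". No other method is named for comparing loads. The software is SPSS 25, and no rule is given for a missing load.

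Under Procedure, each participant breathes against six loads, 30% to 80% of MIP, in random order on one day. The loads are separated by at least 10 minutes of rest. The intensity to carry forward is defined there: "The % of MIP that associates with the highest calculated DTF and a relatively stable change in the activity of accessory muscles". The stated aim concerns the stroke cohort: "To determine the optimal training intensity that is associated with the strongest diaphragmic thickening fraction in people after stroke".

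The second session has one stated purpose: "All research procedures will be repeated again after 2 days to examine the test-retest reliability of ultrasonographic measurements of DTF". The Statistical analysis section gives it an intraclass correlation, to "examine the test-retest reliability coefficient of ultrasonographic measurements of DTF recorded with different inspiratory pressures".

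The Sample size calculation reads: "Considering an effect size of 0.2, an alpha error probability of 0.05 and a power of 0.80, the estimated sample size is 54 participants". It then adds 20% for attrition and arrives at 65 per cohort, 130 in total.

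**The concern.** Classical repeated-measures ANOVA works on participants with a value in every cell. With six cells, one missing value, whether from a load not completed or an unusable image, removes the other five from that person. A modest miss rate per load can therefore become a much larger loss of people.

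Two things would be at stake. The first is precision. The conclusion is a choice among neighbouring loads, so it depends on contrasts such as 60% against 70% of MIP more than on the overall test. The second is bias. If those who fail a high load differ in DTF from those who complete it, the completers' load profile is not that of the cohort.

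**Working it through.** **1. The plan's own figures.** 54 × 1.2 = 64.8, rounded up to 65; 2 × 65 = 130. The inflation reproduces. The 54 depends on G*Power settings that are not stated. With six measurements, f = 0.2 and sphericity, the within-person test needs 55 people at load correlation 0 and 28 at 0.5. The margin for loss is 65 − 54 = 11 per cohort.

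**2. Loss of people.** Let p be the chance that any one load is missing, independently (assumed; the documents give no rate). The number with all six loads is 65 × (1 − p)^6.

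| p per load | complete of 65 |
|---|---|
| 0 | 65 |
| 1% | 61 |
| 2% | 58 |
| 3% | 54 |
| 5% | 48 |
| 10% | 35 |

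The margin of 11 is used up at p = 1 − (54/65)^(1/6) = 0.030. If the same people miss several loads, the loss is only the number of those people.

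**3. Standard error at p = 3%.** Two hand calculations bracket the gain.

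- Using everyone who has both loads of a contrast: 65 × 0.97² = 61.2 people against 65 × 0.97^6 = 54.1. The SE ratio is √(54.1/61.2) = 0.94, or 6% lower.
- If nothing at all were lost: √(54.1/65) = 0.91, or 9% lower. This cannot quite be reached.

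Simulation falls inside the bracket. With n = 65, load correlation 0.5 and maximum likelihood with unstructured covariance on session 1, the SD of the 60 v 70 contrast was 0.126 to 0.128, against 0.137 to 0.138 for complete cases. The ratios are 0.92 to 0.93, or 7 to 8% lower. A separate simulation gave about 6%. The range is thus about 6 to 8% lower with the likelihood model. Read the other way, the complete-case SE is larger by 1/0.94 to 1/0.92, about 6 to 9%.

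At other rates the likelihood variance is about 0.95 of the complete-case variance (p = 1%) and 0.75 to 0.78 (p = 5%). These correspond to SEs about 3% and 12 to 13% lower.

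**4. Bias.** Suppose missing the 80% load depends on a person's DTF at 60%. If completers' mean DTF at 60% is shifted by δ SD, their mean at 70% is shifted by about ρδ, where ρ is the load correlation. The complete-case 60 v 70 contrast is then off by (1 − ρ)δ. A simulation of this kind gave a bias of about 0.09 SD for complete cases and close to none for the likelihood model. At ρ = 0.5 that implies δ = 0.09/0.5 = 0.18 SD.

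The size depends on how many miss and how selectively. Under the sharpest dependence, where exactly the lowest fraction x at 60% miss the 80% load, δ = φ(z)/(1 − x), with z the normal quantile of x:

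- x = 3%: 0.068/0.97 = 0.070, bias 0.035 SD
- x = 10%: 0.175/0.90 = 0.195, bias 0.10 SD

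For scale, the SE of this contrast with 54 complete cases is √(2 × 0.5/54) = 0.136 SD.

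**5. Overall test.** The noncentrality is f² × n × 6/(1 − ρ). At ρ = 0.5 it is 0.04 × 54 × 6/0.5 = 25.9 for n = 54 and 31.2 for n = 65, giving power 0.986 and 0.996. At ρ = 0 power is 0.795 and 0.875.

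**The case against.** The strongest reply is that nothing here is wrong. The ANOVA is valid with complete data. The protocol describes 10 breaths per load with rest between loads, and no passage says that loads go uncompleted. The 3% is a break-even rate, not an estimate. Even if the margin is used up, the 54 who remain are the plan's own target, and at load correlation 0.5 the overall test barely notices. All of this stands, and it is why the point is an improvement only.

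A reader might infer four stronger things that the documents do not support.

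- **That the plan prescribes deletion.** It does not. Deletion follows from the standard procedure when no other rule is written.
- **That high loads will be missed and the chosen load distorted.** The Introduction links loads above 60% of MIP to accessory-muscle activation and fatigue, but in healthy adults and ventilated patients, and it does not speak of failure to complete. Bias is conditional on selective missingness.
- **That the study is underpowered.** Step 5 does not show this; power depends on a load correlation that the plan does not state.
- **That the second session is wasted and should be pooled into the main analysis.** It has a deliberate reliability role, and because all procedures are repeated, MIP and hence the absolute pressures may be reset. With complete data, pooling would multiply the SE of a load contrast by √((1 + r)/2), which is 0.87, 0.94 or 0.97 at between-session correlation r of 0.5, 0.75 or 0.9. But if a load-by-session pretest decides whether to pool, the chance of picking the true best load rises by only about 3, 1 or 0.5 percentage points (f = 0.2, assumed peak at 60%, load correlation 0.5). At r = 0.5, if the peak moves by one load between sessions, that rule picks the session-1 best load less often than session 1 alone (54.1% against 56.2%).

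**Conclusion.** The point holds as a cheap improvement. The plan leaves missed loads unaddressed, and its only named method would by default discard partly observed participants. The gain depends wholly on a miss rate that the documents do not give: nil with no missed loads, and an SE about 6 to 8% lower at an assumed 3% per load missed independently, with load correlation 0.5.

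Protection against bias is a further benefit, but only when missingness depends on DTF values that were observed. If people fail a high load because of what their response at that load would have been, neither analysis is safe. A mixed model also cannot recover anyone who leaves before the first load.

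**What to change.** In the Statistical analysis section:

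- In each cohort, with the stroke cohort answering the aim, and for each side separately, make the main DTF and sEMG load comparison a linear mixed model (SPSS MIXED) on all available first-session loads. Use load (categorical) and order position as fixed effects and an unstructured covariance across the six loads. State that session 1 is the source.
- Report the complete-case repeated-measures ANOVA with Greenhouse-Geisser correction as a sensitivity analysis.
- Report non-completion by load and cohort, so that the missing-at-random assumption can be judged.
- Keep session 2 for the intraclass correlation. A pooled two-session DTF model with participant-by-load effects may be added as a sensitivity analysis, with no pretest deciding the primary result.

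The cost is analysis time only, with no new data or software. There are eight main fits (2 cohorts × 2 sides × 2 outcomes), each with 6 × 7/2 = 21 covariance parameters on about 65 people. The simulations used purpose-written maximum-likelihood code, so convergence in SPSS is untested; a fallback covariance should be named in advance. The model relies on missing at random.
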